2. OBJECTIVE

Primary Objective: To evaluate the use of NIR/US to predict and assess pathological response of breast cancer patients undergoing NAC.

Exploratory Objective: To evaluate the use of NIR/US to predict treatment response, measured by PEPI score (0 vs not), in breast cancer patients undergoing NAE.

Additional Objective: To compare the results of NIR/US to predict and assess pathological response in patients undergoing neoadjuvant treatment with CEM in the subset of patients who have undergone CEM as part of their standard of care evaluation.

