Following each patient study, the near infrared images will be reconstructed by [name] group who will not know the final pathological response. At the end of this two-year trial, the near infrared data will be pooled for final statistical analysis. In the subset of patients who have had CEM as part of their clinical care, to compare results of NIR-US with CEM. In particular to correlate the presence and extent of enhancement at the malignant site with total hemoglobin concentration (tHb).

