7. DATA COLLECTION AND ANALYSIS

Study specific data will be collected from subjects after informed consent is obtained. The key data elements will likely include:

- Pathology results from initial diagnosis, during neoadjuvant treatment and final surgical management with specific attention to Miller Payne pathologic response (see below)
- Neoadjuvant Treatment information, including: medication regimen, frequency, relevant basic lab results and complications
- Imaging results from the serial US exams conducted during the NIR visits
- NIR results
 - Comparison of CEM with NIR in subset with CEM exam

In some cases, the pathologist may review existing biopsy specimens with special staining to look for signs of increased blood supply and vessel density. This will not require additional slicing of standard of care biopsy specimens; thus, samples will not be labeled or stored for the research study. The results of these tests will not be placed in the patient medical record. The results of these tests may be given to the investigators to correlate to the results of the NIR/US procedures.

The biopsy grading was based on Miller-Payne system [19]. In the Miller-Payne system, the pathologic response is divided into 5 grades based on comparison of tumor cellularity between pre-neoadjuvant core biopsy and definitive surgical specimen as:

- grade 1: no change or some alteration to individual malignant cells but no reduction in overall cellularity (pNR)

- grade 2: a minor loss of tumor cells but overall cellularity still high; up to 30% (pPR)
- grade 3: between an estimated 30% and 90% reduction in tumor cells (pPR)
- grade 4: a marked disappearance of tumor cells such that only small clusters or widely dispersed individual cells remain (almost pCR); more than 90% loss of tumor cells
- grade 5: no malignant cells identifiable in sections from the site of the tumor; only vascular fibroelastotic stroma remains often containing macrophages (pCR) (however, ductal carcinoma *in situ* (DCIS) may be present)

[name], specialist in breast pathology, will assess patient treatment responses and provide Miller-Payne scores as well as other pathological findings from patients' standard of care assessments.

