7.1. Data Analysis and Validation

In our early study, among the 32 patients (recruited from 2007 to 2011) from whom data was reported in Ref. 18, 24 HER2 negative patients (75%) were treated with a Taxol-based regimen and five HER2 positive patients (16%) were treated with Herceptin-based regimens. The rest three were treated with a Taxol-based regimen in combination with bevacizumab. This anti-angiogenesis regimen was stopped by the FDA later due to its side effects.

The primary goal of this study is to assess the predictive value of NIR/US in monitoring early tumor vasculature and oxygen changes and to correlate these changes with patients' pathological response. We observed that the Her2+ patients, triple receptor negative patients, and ER+ patients treated with different regiments respond differently. Based on small sample size of Her2+ patients (n=5), triple receptor negative patients (n=6), and ER+ and Her2- patients (n=22), the early changes in total hemoglobin level were observed at different treatment cycles. Our goal in this study is to extend the pilot study into a larger patient pool for Her2+, triple receptor negative and ER+, Her2- patients and benchmark the optical signature of neoadjuvant treatment response of subsets of breast cancer based on molecular phenotype.

A secondary goal of this study is to assess the correlation of optical imaging parameters with the presence and intensity of contrast enhancement of the index malignancy in patients who have undergone CEM.

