10.2. Primary Endpoint

The primary endpoint is pathologic response based on the Miller-Payne grading system (See Section 7 for description on grade 1~5). Patients will be grouped into responder (grade 4/5) and non-responder (grade 1~3) for statistical analysis.

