10.3. Data Analysis

The multivariate logistic regression models will be used to model the binary primary endpoint. The receiver operating characteristics (ROC) curve analysis will be applied based on the fitted multivariate logistic model to evaluate the predictive ability of tumor vascularity parameters measured by NIR/US at baseline and at different treatment cycles including total, oxygenated and deoxygenated hemoglobin concentrations (abbreviated as tHb, oxyHb, deoxyHb, respectively) without and with inclusion of classic pathological variables including tumor histology, estrogen and progesterone receptor status, HER2

status, Ki67 proliferation index, Nottingham score, mitotic index, intrinsic subtype. To summarize the resulting predictive ability, the area under ROC (AUC) with DeLong's method for confidence interval calculation and the sensitivity, specificity, positive and negative predictive value corresponding to an optimal cutoff will be derived. Two models will be compared based on their AUCs based on the DeLong's method and the likelihood ratio test. To robustly assess the predictive ability, the cross validation (CV) procedure will be applied: at each CV, 2/3 of the observations will be used to train the model while the remaining will be used to validate the model.

For the exploratory neoadjuvant endocrine cohort, the analysis will also include correlation with PEPI scores.

For the additional aim, correlate tHb with enhancement on CEM.

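### The CEM objective concerns pathological response, but its only planned analysis correlates tHb with CEM enhancement and leaves response out

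*Combined protocol and SAP*

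**What the plan says.** Section 2 gives the additional objective as "To compare the results of NIR/US to predict and assess pathological response in patients undergoing neoadjuvant treatment with CEM in the subset of patients" who had CEM as part of standard care. Pathological response is the subject of that comparison.

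The later sections describe something narrower:

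- Section 6 announces a comparison of NIR/US with CEM and then specifies it: "In particular to correlate the presence and extent of enhancement at the malignant site with total hemoglobin concentration (tHb".
- Section 7 lists a data item, "Comparison of CEM with NIR in subset with CEM exam", with no method, time point or outcome.
- Section 7.1 states a secondary goal, to "assess the correlation of optical imaging parameters with the presence and intensity of contrast enhancement of the index malignancy". Response is not mentioned.
- Section 10.3 closes with "For the additional aim, correlate tHb with enhancement on CEM".

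For the primary question, Section 10.2 defines the binary outcome: "Patients will be grouped into responder (grade 4/5) and non-responder (grade 1~3) for statistical analysis". Section 10.3 then adds that "Two models will be compared based on their AUCs", using DeLong's method and a likelihood ratio test. Those models contain the NIR/US parameters without and with the classic pathological variables. CEM is in neither.

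**The concern.** CEM is the only imaging method named as a comparator in the objectives, and Section 1.1 describes it as promising for assessing neoadjuvant response. A reader of Section 2 will expect some statement of how the two methods relate to pathological response in the same patients. The planned statistic has no response variable in it, so it cannot supply one.

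The correlation itself is also under-specified. NIR/US follows the visit tables in Sections 5.1 and 5.2 and gives up to six tHb values per patient. CEM appears in neither table and is done whenever standard care calls for it. Nothing says which tHb value belongs with which CEM, or whether the CEM measure is presence, extent (Section 6) or intensity (Section 7.1) of enhancement. Those choices would be made after the data are seen.

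**Working it through.** The documents give no figure, sample size or error rate for the CEM aim, so there is no stated result to reproduce. The check has three parts.

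**1. Objective against analysis.** Section 2 involves three quantities: NIR/US, CEM and pathological response. Sections 6, 7.1 and 10.3 specify a relation between the first two only. The primary analysis in Section 10.3 relates NIR/US to response. The missing link is CEM to response, and no section supplies it.

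**2. Does the correlation determine relative accuracy?** Assumptions, none from the documents: responder fraction p = 0.40; both measures normal with unit variance within each response group; overall correlation R = 0.60.

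- Separation of the groups on a test: d = √2 × Φ⁻¹(AUC). AUC 0.65, 0.75 and 0.85 give d = 0.545, 0.954 and 1.466.
- With v = p(1 − p) = 0.40 × 0.60 = 0.24 and w the within-group correlation, R = (w + v·d₁·d₂) / √[(1 + v·d₁²)(1 + v·d₂²)].
- AUCs 0.75 and 0.75: v·d₁·d₂ = 0.24 × 0.910 = 0.218 and the denominator is 1.218. With w = 0.51, R = 0.728 / 1.218 = 0.60.
- AUCs 0.85 and 0.65: v·d₁·d₂ = 0.24 × 0.799 = 0.192 and the denominator is 1.231 × 1.035 = 1.274. With w = 0.57, R = 0.762 / 1.274 = 0.60.
- AUCs 0.65 and 0.85: the same by symmetry.

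A simulation of 400,000 patients per case agreed: R of 0.600, 0.599 and 0.599, with AUCs within 0.001 of target. One value of the planned statistic therefore fits equal accuracy or a clear advantage for either method.

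**3. What a direct comparison could deliver.** Section 10.1 expects about 50 completers from 60 enrolled (60 × 0.80 = 48, consistent), so about 50 is the ceiling for the CEM subset. Its actual size is not given. Under the assumptions in part 2, with 3,000 replicates per row, a two-sided 0.05 level and true AUCs of 0.85 and 0.65 (difference 0.20):

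| Patients with both tests | Power of paired DeLong test | Median 95% half-width | 0.20 ± half-width |
|---|---|---|---|
| 10 | 14% | 0.35 | -0.15 to 0.55 |
| 20 | 39% | 0.23 | -0.03 to 0.43 |
| 30 | 57% | 0.18 | 0.02 to 0.38 |
| 50 | 84% | 0.14 | 0.06 to 0.34 |

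For AUCs of 0.85 and 0.75, power is about 5%, 11%, 18% and 28%. A direct comparison is therefore an estimate to describe, not a test to rely on.

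**The case against.** The strongest reply is that Sections 6, 7.1 and 10.3 agree with one another, and Section 2 is the outlier. On that view the authors meant an association all along, and the defect is a loosely worded objective. This is a fair reading, and it is why rewording Section 2 is an acceptable remedy. It does not remove the mismatch: one of the two texts has to change.

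Several stronger readings are tempting, and the documents do not support them:

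- *That the objective asks which method predicts better.* It asks for a comparison of results and does not use those terms.
- *That the comparison is impossible.* Miller-Payne grade is collected (Sections 7 and 10.2), so it can be made in patients with CEM. It is unspecified.
- *That mixing treatment stages manufactures a positive correlation.* Pooling pairs across stages can inflate a correlation if both measures share a treatment trend, while pairing values from different stages would typically weaken it. The documents do not establish that both measures fall under treatment. What stands is that no time point or pairing rule is given.
- *That the trial intends to claim equivalence or inferiority.* No section proposes this.

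It can also be said that a paired AUC comparison in an opportunistic subset would be imprecise. It would, as the table shows. An imprecise estimate of the right quantity, with its interval, still bears on the objective, whereas the correlation alone does not.

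**Conclusion.** The point holds in this form: Section 2 states a comparison concerning pathological response, and the only analysis planned for it omits response. The non-identification in part 2 of the working is a matter of principle. The particular AUC pairs rest on the assumed 40% responders, binormal measures and correlation of 0.6, and show what is possible, not what is likely in this trial. The missing pairing rule is a second, smaller gap whose effect could go either way.

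This is an additional objective in a subset of unstated size, with no power claim attached. The primary endpoint and its analysis are untouched. The change should be made before the CEM data are analysed, but nothing else in the trial depends on it.

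**What to change.** Choose one of two routes.

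**If a comparison is intended**, replace the closing sentence of Section 10.3 with text to this effect:

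- Name one CEM predictor (for example, extent of enhancement) and one NIR/US parameter (tHb, stating whether absolute or as change from baseline).
- Pair each CEM with the nearest NIR/US scan in the same treatment phase, such as baseline with baseline or pre-surgery with pre-surgery. Use one pair per patient in each phase analysed.
- In chemotherapy patients with both tests, report each test's AUC for Miller-Payne 4/5 versus 1-3 and the paired DeLong difference with its 95% confidence interval, labelled descriptive.
- Report the number of patients with CEM and the number of usable pairs.
- Keep the correlation of tHb with enhancement as a secondary result, given separately by treatment phase.
- State that the endocrine cohort contributes only to the correlation. Section 2 refers to neoadjuvant treatment in general, so this limit should be explicit.

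**If only an association is intended**, reword the additional objective in Section 2 to say so, add the predictor and pairing rule to Section 10.3, and state that no comparative conclusion about response prediction will be drawn.

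The cost is a few sentences and, on the first route, one small analysis using the plan's own endpoint and DeLong's method on data already to be collected. The drawbacks are a probably wide interval and the loss of CEM examinations with no NIR/US scan in the same phase.
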